10.4 Appendix 4: Contraceptive Guidance and Collection of Pregnancy Information

Definitions

WOCBP

A woman is considered fertile following menarche and until becoming post-menopausal unless permanently sterile (see below).

Women in the following categories are not considered WOCBP:

1. Premenarchal
2. Premenopausal female with one of the following:
 - Documented hysterectomy

- Documented bilateral salpingectomy
- Documented bilateral oophorectomy

NOTE: Documentation can come from the site personnel's review of the participant's medical records, medical examination, or medical history interview.

3. Post-menopausal female

- A post-menopausal state is defined as no menses for 12 months without an alternative medical cause. A high follicle-stimulating hormone (FSH) level in the post-menopausal range may be used to confirm a post-menopausal state in women not using hormonal contraception or hormonal replacement therapy (HRT). However, in the absence of 12 months of amenorrhea, a single FSH measurement is insufficient.
- Females on HRT and whose menopausal status is in doubt will be required to use one of the non-estrogen hormonal highly effective contraception methods if they wish to continue their HRT during the study. Otherwise, they must discontinue HRT to allow confirmation of post-menopausal status before study enrollment.

Contraception Guidance:

Male Participants:

Male participants with female partners of childbearing potential are eligible to participate if they agree to ONE of the following during the protocol-defined time frame in [Section 5.1](#):

- Are abstinent from penile-vaginal intercourse as their usual and preferred lifestyle (abstinent on a long-term and persistent basis) and agree to remain abstinent.
- Agree to use a contraceptive method with a failure rate of <1% per year as described in the table below when having penile-vaginal intercourse with a WOCBP who is not currently pregnant.

In addition, male participants must refrain from donating sperm for the duration of the study and for 3 months after the last dose of study treatment.

Male participants with a pregnant or breastfeeding partner must agree to remain abstinent from penile-vaginal intercourse or to use a male condom during each episode of penile penetration during the protocol-defined time frame.

Female Participants

Female participants of childbearing potential are eligible to participate if they agree to use a highly effective method of contraception consistently and correctly as described in the table below.

| Highly Effective Contraceptive Methods That Are User Dependent¹ |
|---|
| Failure rate of <1% per year when used consistently and correctly. |
| Combined (estrogen- and progestin-containing) hormonal contraception associated with inhibition of ovulation ² 
• Oral• Intravaginal• Transdermal |
| Progestogen-only hormonal contraception associated with inhibition of ovulation 
• Oral• Injectable |
| Highly Effective Contraceptive Methods That Are User Independent¹ |
| Implantable progestogen-only hormonal contraception associated with inhibition of ovulation 
• IUD• Intrauterine hormone-releasing system (IUS)• Bilateral tubal occlusion |
| Vasectomized partner |
| A vasectomized partner is a highly effective contraception method provided that the partner is the sole male sexual partner of the WOCBP and the absence of sperm has been confirmed. If not, an additional highly effective method of contraception should be used. |
| Sexual abstinence |
| Sexual abstinence is considered a highly effective method only if defined as refraining from heterosexual intercourse during the entire period of risk associated with the study treatment. The reliability of sexual abstinence needs to be evaluated in relation to the duration of the study and the preferred and usual lifestyle of the participant. |

NOTES:

1 Typical use failure rates may differ from those when used consistently and correctly. Use should be consistent with local regulations regarding the use of contraceptive methods for participants participating in clinical studies.

Pregnancy Testing

- WOCBP should only be included after a confirmed menstrual period and a negative highly sensitive serum pregnancy test.
- An additional serum pregnancy testing should be performed at Visit 5 (EOS).
- Pregnancy testing will be performed whenever a menstrual cycle is missed or when pregnancy is otherwise suspected.

Collection of Pregnancy Information:

Male participants with partners who become pregnant

- The Investigator will attempt to collect pregnancy information on any male participant's female partner who becomes pregnant while the male participant is in this study. This applies only to male participants who receive study treatment.
- After obtaining the necessary signed informed consent from the pregnant female partner directly, the Investigator will record pregnancy information on the appropriate form and submit it to the Sponsor within 24 hours of learning of the partner's pregnancy. The female partner will also be followed to determine the outcome of the pregnancy. Information on the status of the mother and child will be forwarded to the Sponsor. Generally, the follow up will be no longer than 6 to 8 weeks following the estimated delivery date. Any termination of the pregnancy will be reported regardless of fetal status (presence or absence of anomalies) or indication for the procedure.

Female participants who become pregnant

- The Investigator will collect pregnancy information on any female participant who becomes pregnant while participating in this study. Information will be recorded on the appropriate form and submitted to the Sponsor within 24 hours of learning of a participant's pregnancy. The participant will be followed to determine the outcome of the pregnancy. The Investigator will collect any follow up information on the participant and the neonate and the information will be forwarded to the Sponsor. Generally, follow up will not be required for longer than 6 to 8 weeks beyond the estimated delivery date. Any termination of the pregnancy will be reported, regardless of fetal state (presence or absence of anomalies) or indication for the procedure.

- While pregnancy itself is not considered to be an AE or SAE, any pregnancy complication or elective termination of a pregnancy will be reported as an AE or SAE. A spontaneous abortion is always considered to be an SAE and will be reported as such. Any post-study pregnancy-related SAE considered reasonably related to the study treatment by the Investigator will be reported to the Sponsor as described in [Section 8.3.4](#). While the Investigator is not obligated to actively seek this information in former study participants, he or she may learn of an SAE through spontaneous reporting.
- Any female participant who becomes pregnant while participating in the study will be withdrawn from the study.

10.5 Appendix 5: List of Abbreviations

| | |
|-------------------|--|
| AHI | apnea-hypopnea index |
| AE | adverse event |
| Bang | Body mass index, Age, Neck circumference, and Gender criteria |
| BMI | body mass index |
| CFR | Code of Federal Regulations |
| CNS | central nervous system |
| CPAP | continuous positive air pressure |
| CSSA | Cocaine Selective Severity Assessment |
| CYP2D6 | cytochrome P450 2D6 |
| CYP3A4 | cytochrome P450 3A4 |
| DSM-5 | Diagnostic and Statistical Manual of Mental Disorders, 5th edition |
| ECG | electrocardiogram |
| EEG | electroencephalogram |
| eCRF | electronic case report form(s) |
| EDC | electronic data capture |
| EMG _{gg} | genioglossal electromyographic |
| EOS | end of study |
| ESS | Epworth Sleepiness Scale |
| FSH | follicle-stimulating hormone |
| GCP | Good Clinical Practice |
| | |
| HRT | hormone replacement therapy |
| ICF | informed consent form |
| ICH | International Conference on Harmonisation |
| IEC | Independent Ethics Committee |
| IND | Investigational New Drug |
| IPSS | International Prostate Symptom Score |
| IRB | Institutional Review Board |
| IRT | Interactive Response Technology |
| OSA | obstructive sleep apnea |
| OTC | over-the-counter |
| MAOI | monoamine oxidase inhibitor |
| NREM | non-rapid eye movement |
| PGI-S | Participant Global Impression of Severity |

| | |
|-------|---|
| PK | pharmacokinetic(s) |
| PSG | polysomnography |
| DWRT | Delayed Word Recall Test |
| QHS | 1 dose every night at bedtime |
| REM | rapid eye movement |
| SAE | serious adverse event |
| SAP | Statistical Analysis Plan |
| SoA | Schedule of Activities |
| STOP | Snoring, Tiredness, Observed apnea, and Blood pressure criteria |
| SUSAR | suspected unexpected serious adverse reaction |
| ULN | upper limit of normal |
| US | United States |
| WOCBP | woman of childbearing potential |

11 References

| PGI-S | Participant Global Impression Of Severity |
| PK | Pharmacokinetic(S) |
| PSG | Polysomnography |
| REM | Rapid Eye Movement |
| SAE | Serious Adverse Event |
| SaO ₂ | Oxygen Saturation |
| SAP | Statistical Analysis Plan |
| SoA | Schedule Of Activities |
| STOP | Snoring, Tiredness, Observed Apnea, And Blood Pressure Criteria |
| SUSAR | Suspected Unexpected Serious Adverse Reaction |

1 INTRODUCTION

The purpose of this Statistical Analysis Plan is to describe the planned analyses and reporting for Sponsor protocol APN-002 (240495), entitled “Phase 2, Placebo-Controlled, Parallel Group Dose-Finding Study to Evaluate the Efficacy and Safety of Three Fixed-Dose Combinations of AD036 in Adults with Obstructive Sleep Apnea.

This Phase 2B clinical study is designed to examine the efficacy and safety of AD036 (combination of atomoxetine and oxybutynin) at concentrations that are both similar to the concentration used in the first in human study, and at 2 lower doses, versus placebo. Overall, the study is expected to provide dose selection guidance and a deeper understanding of repeat-dose safety and tolerability for the ongoing clinical development of AD036.

The analyses described in this SAP are based upon the following study documents:

- Study Protocol, Version 1.4 (Dec 04, 2018)
- Electronic Case Report Form (eCRF), Version 1.0 (Jan 31, 2019)

The structure and content of this SAP provides sufficient detail to meet the requirements identified by the Food and Drug Administration (FDA), European Medicines Agency (EMA), and International Conference on Harmonization (ICH) of Technical Requirements for Registration of Pharmaceuticals for Human Use: ICH Harmonized Tripartite Guideline Statistical Principles for Clinical Trials E9 [1]

The SAP will be finalized prior to database lock and describes the statistical analysis as it is foreseen when the study is being planned. If circumstances should arise during the study rendering this analysis inappropriate, or if improved methods of analysis should arise, updates to the analyses may be made. Any deviations from the SAP after database lock, reasons for such deviations and all alternative or additional statistical analyses that may be performed, will be described in an SAP Addendum. In this SAP, terminologies like Subjects, Participant or Patients means participants enrolled in the study.

2 STUDY OBJECTIVES

2.1 Primary Objective(s)

1. To assess the efficacy of 3 different fixed doses of AD036 (the combination of atomoxetine and oxybutynin) vs. placebo.
2. To evaluate safety and tolerability of the combination AD036.

3 INVESTIGATIONAL PLAN**3.1 Overall Study Design and Plan**

This is a phase 2, randomized, double blind, placebo-controlled, repeat-dose, parallel arm, outpatient and inpatient, multi-center, dose finding study of the combination of atomoxetine and oxybutynin in adults with obstructive sleep apnea (OSA) documented by polysomnography (PSG).

Number of Participants and Randomization: Approximately 140 participants will be randomized to study treatment in equal ratio (1:1:1:1), at least 35 participants per arm, to 1 of 4 parallel treatment groups. At a study site, multiple randomizations may occur within a single arm in a short period of time, temporarily leaving no investigational product available for the given study arm while resupply is sent from the depot. Consequently, if a subsequent randomization is to the same study arm, that randomization number will be skipped, and the patient will be randomly allocated to the next free number in the randomization list corresponding to one of the treatments in stock at the site, i.e. “forced randomization”. Skipped randomization numbers will remain unallocated.

[figure not shown]
Treatment Groups and Duration: There will be 4 parallel treatment groups, as follows:

| Group | Atomoxetine/oxybutynin (mg) | Subjects (n) |
|-------|-----------------------------|--------------|
| 1 | 75/5 | 35 |
| 2 | 75/1.5 | 35 |
| 3 | 25/5 | 35 |
| 4 | Placebo | 35 |

Overall study duration will be up to 8-9 weeks, with up to 28 days for screening and baseline PSG. All participants will receive placebo for 2 days to establish baseline measures. Participants assigned to active treatment will subsequently receive low dose (25 mg atomoxetine/1.5 mg oxybutynin) for a 3-day dose-escalation period. Participants randomized to placebo will have a placebo run-in period.

Following the dose-escalation period, participants will receive the dose level to which they were randomized (75/5; 75/1.5; 25/5; placebo) for 7 (± 2) nights (6 nights at home, seventh night inpatient PSG). On the final night of dosing, participants will return for inpatient PSG (Visit 4). A follow-up safety visit will take place 2 weeks post study treatment dosing (± 2 days), or upon early withdrawal (figure 1).

Dosing of the study treatment will occur approximately 30 minutes prior to bedtime. Participants who withdraw from the study will not be replaced.

Figure 1 – Overall Study design

Abbreviations: ATO = atomoxetine; EoS = end of study; OXY = oxybutynin; PSG = polysomnography

3.2 Endpoints and Associated Variables

3.2.1 Primary Efficacy Endpoint

Comparison of the proportion of participants with $\geq 50\%$ reduction in apnea-hypopnea index (AHI) from baseline to the second PSG visit in the atomoxetine 75 mg/oxybutynin 5 mg dose group compared with placebo.

3.2.2 Primary Safety & Functional Endpoints

Safety Endpoints

1. The number and percentage of participants reporting Adverse Events (AEs), including the post-dosing period
2. Change from baseline in physical examination findings
3. Change from baseline in clinical laboratory testing (hematology, serum chemistry, urinalysis, other tests)
4. Cocaine Selective Severity Assessment (CSSA) results, Modified for study treatment
5. Prospective Suicidality Assessment (item 17 “suicidality” of CSSA) results

6. Change from baseline in PSG parameters: heart rate, electrocardiogram (ECG), electroencephalogram (EEG), oximetry
7. Change from baseline in vital signs, ECG

Functional Endpoints

1. Digit Symbol Substitution Test (DSST) results
2. Delayed Word Recall Test (DWRT) results

3.2.3 Secondary Efficacy Endpoints

1. Percent change AHI, high-dose arm (atomoxetine 75 mg/oxybutynin 5 mg dose) vs. placebo.
2. Proportion of participants with $\geq 50\%$ reduction in AHI, measured in the supine sleeping position, from baseline to the second PSG visit in the 75/5 dose group compared with placebo.
3. Proportion of participants with $\geq 50\%$ reduction in Oxygen desaturation index from baseline (average of 2 baseline nights) to study treatment nights (average of 6 nights) for the 75/5 dose group compared with placebo.
4. Change from baseline in the Epworth Sleepiness Scale (ESS) from baseline to the second PSG visit in the 75/5 dose group compared with placebo.
5. Change from baseline in the Participant Global Impression of Severity (PGI-S) from baseline to the second PSG visit in the 75/5 dose group compared with placebo.
6. Proportion of participants with $\geq 50\%$ improvement in AHI from baseline to the second PSG visit in the 75/5 dose group compared with the lower treatment dose of 25/5.
7. In the case that a statistically significant result for the AHI comparison of dose 75/5 to 25/5 is observed, then the proportion of participants with $\geq 50\%$ improvement in AHI from baseline to the second PSG visit in the 75/5 dose group compared with the lower treatment dose of 75/1.5.

3.2.4 Tertiary/Exploratory Endpoints

1. Proportion of participants with $\geq 50\%$ AHI decrease and final AHI $< 15/\text{hour}$, PSG nights
2. Total time with oxygen saturation (SaO_2) $< 90\%$, PSG nights
3. Total time with $\text{SaO}_2 < 80\%$, PSG nights
4. Snoring index, PSG nights

5. Sleep stages distribution and % of time in the various sleep stages, PSG nights
6. Arousal index, PSG nights
7. Oxygen desaturation index, low-dose run in vs baseline, at home nights
8. Proportion of apneas to hypopneas
9. Proportion of participants with $\geq 50\%$ improvement in AHI from baseline to the second PSG visit
10. Correlation of phenotypic traits (Vpassive, Vactive, arousal threshold and Loop gain) with AHI response or subjective outcomes

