5.1 Inclusion Criteria

Participants are eligible to be included in the study only if all of the following criteria apply:

Age and Sex

1. Male participants between 25 to 65 years of age or female participants between 25 to 70 years of age, inclusive, at the Screening Visit.

Type of Participant and Disease Characteristics

2. Participants are eligible for screening PSG if any of the following:
 - Prior history of diagnosis of OSA of a severity for which CPAP is typically recommended (according to International Classification of Sleep Disorders, Version 3 criteria) at any time in the past (participant self-report acceptable if medical records unavailable); or, for participants without a prior diagnosis of OSA, participants are eligible for screening if the Snoring, Tiredness, Observed apnea, and Blood pressure (STOP), and Body mass index, Age, Neck circumference, and Gender (Bang) score is ≥ 5 , or $STOP \geq 2 + \text{body mass index (BMI)} > 35 \text{ kg/m}^2$.
 - CPAP intolerance or poor compliance (compliance is defined as use of CPAP 4 hours per night for 70% of nights; per participant self-report); or CPAP-naïve.
 - Participants who had been using CPAP at least 4 hours nightly for at least 70% of the nights are eligible for further screening and baseline PSG for this study only if CPAP will not have been used for 1 month prior to the screening/baseline PSG for this study.
3. $AHI \geq 20$ on screening PSG, based on initial reading the night of Screening PSG¹.

¹ The assessment of the PSG technician at the time of PSG recording is used to determine PSG eligibility criteria including AHI, central apnea index, and periodic limb movement arousal index; for the purposes of study endpoint analysis, the results of the PSG centralized reading will be used.

4. Epworth Sleepiness Scale (ESS) score ≥ 4 for participants not using CPAP.
5. Previous surgical treatment for OSA is allowed if ≥ 1 year prior to enrollment.
6. If male, International Prostate Symptom Score (IPSS) must be less than 15.

Weight

7. BMI between 18.5 and 40.0 kg/m², inclusive, at the pre-PSG visit.

Male participants:

8. If male and sexually active with female partner(s) of childbearing potential, participant must agree, from Study Day 1 through 1 week after the last dose of study drug, to practice the protocol specified contraception (see [Appendix 4](#): Contraceptive Guidance and Collection of Pregnancy Information).

Female participants:

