4.5 General Presentation Considerations

All statistical analyses will be performed using SAS® software Version 9.3 or later.

Medical history and AEs will be coded using the latest version of MedDRA. The frequency count and percentage of subjects will be summarized according to the coded terms of system organ class (SOC) and preferred term (PT). Subject-wise data listing will be provided.

For participants who are eligible and enroll in the study, the screening PSG night will serve as the baseline measure for AHI and other PSG efficacy and safety endpoints. Baseline measures for additional secondary and tertiary endpoints based on home oximetry will be recorded at home during the placebo period, and these endpoint measures will continue to be collected over the subsequent at-home study treatment dosing period. On the final night of dosing (Visit 4), participants will return for inpatient PSG.

A participant is considered to have completed the study if he/she has completed all phases including Screening (visit 1), Baseline (visit 2), placebo baseline (2 night (Day 1-2), low dose run-in or placebo night (3 night [Day 3-5 +2]), ATO/OXY (mg) or placebo 7 night (Day 6-12 +/- 2) and the final Follow-up visit or the last scheduled procedure shown in the Schedule of Activities (SoA) (Appendix).

The end of the study is defined as the date of the last visit of the last participant in the study or last scheduled procedure shown in the SoA for the last participant in the study globally.

Continuous data will be summarized in terms of the mean, standard deviation (SD), median, minimum, maximum and number of observations, unless otherwise stated.

Continuous data that are expected to be skewed will be presented in terms of the maximum, upper quartile, median, lower quartile, minimum and number of observations. The minimum and maximum will be reported to the same number of decimal places as the raw data recorded in the database. The mean, median, lower quartile and upper quartile will be reported to one more decimal place than the raw data recorded in the database. The SD will be reported to two more decimal places than the raw data recorded in the database. In general, the maximum number of decimal places reported shall be four for any summary statistic.

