4.9.1.2 Adjustments for Covariates

Baseline values for all endpoint will be included as a covariate for all efficacy analysis.

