4.9.1.6 Examination of Subgroups

As a part of the additional exploratory analysis the uniformity of the treatment effect for the primary efficacy variable will be examined for the following subgroups:

1. Subgroup 1 – Baseline AHI Score ≤ 30 and BMI < 35 ,
2. Subgroup 2 - Baseline AHI Score > 30 or BMI ≥ 35

The homogeneity of the treatment effect across subgroups will be investigated. In addition, a statistical test for the presence of a treatment-by-subgroup interaction will be performed, by including the interaction term in the primary analysis model. The treatment-by-subgroup interaction will be investigated at 10% level ($p < 0.10$).

Summaries of the primary efficacy variable by treatment group and subgroup will be produced. No formal statistical analysis will be performed within subgroup.

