Similar analysis will be carried out for following treatment comparison on this efficacy variable.

All statistical tests of hypotheses will be two-sided and will employ a level of significance of $\alpha = 0.05$.

1. 75/1.5 dose arm vs Placebo arm
2. 25/5 dose arm vs Placebo arm
3. 75/5 dose arm vs. 75/1.5 dose arm
4. 75/5 dose arm vs. 25/5 dose arm
5. 75/1.5 dose arm vs 25/5 dose arm

Correlation of phenotypic traits (Vpassive, Vactive, arousal threshold and Loop gain) with AHI response or subjective outcomes

Sponsor's research team and scientific advisors will perform this exploratory analysis using the PSG data to quantify two key contributors to OSA—pharyngeal collapsibility and compensatory muscle responsiveness—that is applicable to diagnostic polysomnography.

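### The SAP's trait analysis is a correlation with no stated placebo contrast, so a trait that only tracks OSA severity can look like a predictor of drug response

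*SAP*

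**What the plan says.** SAP 3.2.4 lists as item 10 a "Correlation of phenotypic traits (Vpassive, Vactive, arousal threshold and Loop gain) with AHI response or subjective outcomes". The only methods text is the last entry of SAP 4.9.4: "Sponsor's research team and scientific advisors will perform this exploratory analysis using the PSG data to quantify two key contributors to OSA". That entry says the quantification is applicable to diagnostic polysomnography. It does not say which arms enter, which visit supplies the traits, how AHI response is scaled, what the comparator is, or which model is fitted. Most neighbouring entries in 4.9.4 name a model, a 75/5 versus placebo comparison and further pairwise comparisons.

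Other provisions bear on it:

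- SAP 4.5: "the screening PSG night will serve as the baseline measure for AHI and other PSG efficacy and safety endpoints".
- Protocol 5.1, criterion 3, requires AHI of at least 20, "based on initial reading the night of Screening PSG". Eligibility uses the technician's reading and the endpoint uses central scoring, but both come from the same night.
- SAP 4.9.1.2: "Baseline values for all endpoint will be included as a covariate for all efficacy analysis". Whether this binds the trait analysis is not said.
- SAP 4.9.1.6, for the baseline AHI/BMI subgroups only: "a statistical test for the presence of a treatment-by-subgroup interaction will be performed, by including the interaction term in the primary analysis model".
- SAP 3.1: "Approximately 140 participants will be randomized to study treatment in equal ratio (1:1:1:1), at least 35 participants per arm".

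**The concern.** A trait is useful for dose or population decisions only if it modifies the drug effect. A correlation with response does not measure that. AHI response is computed from a baseline night that carries its own random error and that also selected the participant, so part of the response is regression to the mean. A trait associated with that night's AHI, or with underlying severity, can inherit a correlation with response that would also appear on placebo. Putting placebo participants into one overall correlation does not help, because a single coefficient still mixes prognosis with effect modification. The trial already has the concurrent placebo arm that separates the two.

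At stake is whether a positive or negative exploratory trait result can be interpreted.

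**Working it through.** **1. The plan's own figure.** The SAP gives no operating figure for the trait analysis. Its one design figure is 90% power with 35 per arm. The exact power of a two-sided Fisher test is 90.7% for 37% versus 5%, and 90.6% for 46% versus 10%. It reproduces, and is used here only for calibration.

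**2. Model.** Let t be a participant's underlying log AHI, b = t + e2 the Visit 2 value and f = t + δ + e4 the Visit 4 value, with night-to-night error SD σ. Log response is y = f − b = δ + e4 − e2. A responder has y ≤ −ln 2 = −0.693.

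- Noise from the plan's 5% placebo response: Φ(−0.693/(σ√2)) = 0.05, so σ = 0.693/(1.645 × 1.414) = 0.298.
- Drug effect from the plan's 37%: Φ((−0.693 + 0.55)/(0.298 × 1.414)) = Φ(−0.34) = 0.37, so δ = −0.55.

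**3. Assumptions not in the documents.** AHI is log-normal with between-participant log SD 0.5. Entry requires AHI ≥ 20 on the baseline night. The drug effect is the same in every active arm. The trait has no relation to the drug effect. The trait-severity correlation is 0.3, 0.5 or 0.7. The test is two-sided at 0.05, the SAP's usual level.

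- Setting A: median AHI 25, σ = 0.298, δ = −0.55 (calibrated before entry selection).
- Setting B: median AHI 30, calibrated after entry selection to 5%/37% (σ = 0.2805, δ = −0.509) and to 10%/46% (σ = 0.3481, δ = −0.561).

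**4. Plain correlation, trait tracking observed baseline AHI.** Percentage of simulated trials with p < 0.05, at trait-baseline correlation 0.3 / 0.5 / 0.7:

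| Response scale | n | Setting A | Setting B |
|---|---|---|---|
| Percent change | 35 | 6 / 7 / 12 | 6–7 / 8–10 / 12–15 |
| ≥50% responder | 35 | 6 / 7 / 10 | 5–6 / 8–9 / 11–13 |
| Percent change | 105 | 9 / 13 / 25 | 8–10 / 16–20 / 30–39 |
| ≥50% responder | 105 | 7 / 10 / 20 | 7–9 / 14–16 / 25–31 |

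The placebo arm alone (n = 35, log ratio, Setting B) shows the same artefact at about 7 / 9–12 / 15–18%, so the drug does not cause it.

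**5. Adding the baseline covariate.** Rewrite y = t + δ + e4 − b.

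- If the trait is a function of b plus noise, then given b it is pure noise. The rate returns to about 5%.
- If the trait is a function of t, it still carries information about t once b is fixed, so the association remains. The adjusted false-positive rate on a proportional scale is about 17 / 48 / 87% with 105 participants (15–17 / 39–48 / 75–86% in a separate run), and 9–10 / 16–20 / 32–39% with 35. It is lower on the responder scale, but still above nominal.

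The direction also differs. A trait tracking observed baseline appears to predict better response. A trait tracking underlying severity appears, on a proportional scale, to predict worse response.

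**6. Interaction against placebo.** Randomisation makes regression to the mean and prognosis the same in each arm, so they cancel in the trait-by-treatment term. For log AHI the term rejects in about 4–6% of trials, with 35 or 105 active participants against 35 placebo, under both trait mechanisms. On absolute AHI change it still rejects in 6–32%, because a constant proportional effect produces larger absolute falls at higher baselines.

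**The case against.** The strongest reply is that this is a specification gap and not a wrong analysis. A reader might infer that the plan leaves placebo out. The documents do not say so: they name no arms at all. Nor does any passage pool the three active arms for this item, or state that the traits come from Visit 2. That reply stands, and it is why the point is worded as an unspecified contrast.

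A reader might also infer that a false finding is close to certain. On absolute AHI reduction with 105 participants, the false-positive rate is 34 / 80 / 99% (Setting A). But the SAP measures AHI response as percent change or as a 50% reduction, and there the inflation is modest in one arm and moderate when pooled.

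The baseline covariate rule in SAP 4.9.1.2 is a fair objection: if it applies, it removes the problem when the trait tracks observed baseline AHI. It does not cover a trait that tracks underlying severity, which is plausible for quantities that the SAP itself treats as contributors to OSA.

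Finally, the item is exploratory, absent from the testing sequence, and states no significance level of its own. That limits the severity. It does not make a correlation able to answer the question.

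**Conclusion.** The point holds as a low-severity improvement. The stated method is a correlation, with no placebo contrast specified, and it cannot separate a trait that predicts drug effect from one that tracks severity. On the SAP's own response scales the false-positive rate is about 6–12% in one arm of 35 and about 7–30% in 105 pooled participants. The upper ends reach 15% and 39% for percent change if the plan's higher 10% placebo response applies. With a baseline covariate and a trait that tracks underlying severity, the rate is about 17–87% with 105 participants.

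These sizes rest on assumed trait-severity correlations of 0.3 to 0.7, log-normal AHI and an equal effect across active arms. The documents supply none of these. The sizes concern AHI only: nothing here quantifies the subjective outcomes, which have their own baselines. A reader might also infer that a spurious trait would steer patient selection in later trials, but no passage commits to that use.

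**What to change.** In SAP 3.2.4 item 10 and the matching entry in 4.9.4:

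- State that the traits come from the Visit 2 polysomnogram.
- Replace the correlation with a model of Visit 4 log AHI in all randomised arms, with baseline log AHI, treatment, trait and trait-by-treatment. Report the interaction against placebo as the result, and say whether it is given by dose arm or for active arms combined.
- Do not use absolute AHI change, where even the interaction is inflated.
- Keep correlations as descriptive displays by arm, placebo included.

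The cost is a few lines of SAP text; no new data are needed. The drawback is that the interaction is less precise than a simple correlation, so a true modifier will be harder to detect with 35 placebo participants.
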